## **1. STUDY DESIGN**

In this pilot study we will use an ultrasound probe that is currently clinically used to assess pituitary anatomy, the Hitachi-Aloka high resolution pituitary transducer to measure left ventricular (LV) septal thickness during cardiopulmonary bypass in the performance of surgical septal myectomy. We will assess if septal thickness can be visualized during the procedure and if it is likely to improve the efficacy and safety of the procedure. The probe has FDA clearance for a variety of intra-operative surgical procedures but will be off-label for this cardiac surgical protocol. Attached is a memo from the manufacturer stating the device does not meet criteria of a “significant risk device” as per 21 CFR 812.3(m).

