## **4. METHODS AND PROCEDURES**

Subjects will be volunteer patients with hypertrophic cardiomyopathy who will be undergoing myectomy from the HCM Program. Before cardiopulmonary bypass the anterior septal thickness at the point of mitral-septal contact will be measured by TEE in 120 degree view. The distance from the aortic annulus of this location will also be noted. With OPIE the PI will measure this thickness at the

site of mitral-septal contact as assessed by the location of the contact lesion (callous) and confirmed by the cm below the aortic annulus. After resection the residual thickness of the septum will be measured both by OPIE and by post-cardiopulmonary bypass TEE. The thickness of the surgical specimen will be measured. The differences between the OPIE and TEE measured septal thicknesses provide the primary data points for the statistical analysis.

We estimate that the cardiopulmonary bypass time of the OPIE will be prolonged 3 minutes. This may be offset by faster myectomy time gained by more confidence of septal thickening. Length of stay should not be prolonged.

We will enroll 10 subjects in this pilot study. Subject participation will be complete after their hospitalization for surgery. No follow-up visits are necessary, outside of the routine post-op care.

In general, results from studies, which use data, collected as part of this research will be preliminary, and the clinical implications of any findings may not be understood for years. Therefore, individual study results will not be disclosed to the patient and/or his or her healthcare provider(s). Data will be stored in a database housed within the Department of Cardiothoracic Surgery. The above mentioned database will be stored until the end of the study in a password protected secure computer server accessible only by the principle investigator, co-investigators and research staff listed for this project.

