#### **Sample size and data analysis:**

Each of the 10 patients will have 4 measurements(OPIE & TEE before cardiopulmonary bypass and OPIE & TEE after cardiopulmonary bypass) in the septum using two techniques (TEE and OPIE Ultrasound Probe). Primary outcome is the the difference between TEE measured septal thickness and the OPIE measured thickness before and after cardiopulmonary bypass. Center tendency parameters(mean, standard deviation) will be reported for each outcome. For example: we will report the mean and standard deviation for the difference between TEE measured septal thickness and OPIE measured thickness before and after cardiopulmonary bypass. The OPIE and TEE measurements will be compared both before and after cardiopulmonary bypass for each of the outcome as well. Accurate myectomy residual thickness is vital for success of this operation. The clinical utility of the OPIE probe will be shown if there is a  $\geq 2$ mm difference (either greater than or less than) between any single OPIE measurement and the TEE measurement either before cardiopulmonary bypass or after cardiopulmonary bypass. Given the critical nature of the assessment of septal thickness, even a 2-4 mm difference in just one patient (10% of patients) is deemed essential information.

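### Visualisation is a stated aim with no outcome: failed OPIE readings have no stated handling, would by default leave the analysis, and utility could be declared from one readable pair of 20

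*Combined protocol and SAP*

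**What the plan says.** Section 1 (Study Design) lists the questions for the pilot, and visualisation comes first: "We will assess if septal thickness can be visualized during the procedure". Section 2 (Objectives) puts the aim more broadly, as the utility of the probe for measuring septal thickness.

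The analysis deals only with differences. Section 4 (Methods and Procedures) says: "The differences between the OPIE and TEE measured septal thicknesses provide the primary data points for the statistical analysis". The paragraph on sample size and data analysis agrees: "Primary outcome is the the difference between TEE measured septal thickness and the OPIE measured thickness before and after cardiopulmonary bypass". These differences are to be summarised by mean and SD.

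That paragraph also takes complete data for granted: "Each of the 10 patients will have 4 measurements", two by OPIE and two by TEE. Utility is shown by a difference of 2 mm or more "between any single OPIE measurement and the TEE measurement either before cardiopulmonary bypass or after cardiopulmonary bypass", and the plan adds that "even a 2-4 mm difference in just one patient (10% of patients) is deemed essential information".

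The documents contain no definition of a readable image, no count or proportion of successful readings, no feasibility threshold and no rule for a failed reading. The only imaging evidence for the septal application is a simulation, described in section 3 (Rationale), which gives no readable rate in patients.

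**The concern.** Whether the probe can image the septum on bypass is a real unknown. Its use here is off-label, and the supporting evidence comes from a simulation. It is also the kind of question that a 10-patient pilot can describe.

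A difference needs two readings. If OPIE gives no usable image there is nothing to subtract, and the case cannot enter the mean, the SD or the 2 mm rule. The planned analysis therefore describes agreement among the readings that succeeded, and nothing in the plan commits the investigators to saying how many did. A report could follow the plan, give a mean difference and a statement of utility, and leave a reader unable to tell whether it rests on ten patients or a few. If readable is defined only after the images have been seen, the definition can also drift.

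**Working it through.** **Inputs from the documents.** 10 subjects (section 4). Four measurements per patient, two of them OPIE (sample size paragraph). Utility rule: one absolute difference of 2 mm or more, in any patient, at either time point (same paragraph).

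**The plan's own figure.** One patient of the 10 enrolled is 1/10 = 10%, which matches. No alpha, power, SD or expected readable rate is stated, so there is nothing else to reproduce.

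**Step 1. What the rule needs.** Each patient gives at most 2 OPIE-TEE pairs, so there are at most 10 × 2 = 20. The rule is met by 1 pair. On its wording, 19 of 20 OPIE readings could fail (19/20 = 95%) and utility could still be declared if the remaining pair differed by 2 mm or more. This needs no distributional assumption.

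**Step 2. What a feasibility count would show.** Exact (Clopper-Pearson) 95% intervals for x readable patients of n = 10 have lower limit Beta(0.025; x, n − x + 1) and upper limit Beta(0.975; x + 1, n − x). For 10/10 the lower limit reduces to 0.025^(1/10) = 0.692.

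| Readable of 10 | Exact 95% CI |
|---|---|
| 10 | 69.2% to 100% |
| 9 | 55.5% to 99.7% |
| 8 | 44.4% to 97.5% |
| 6 | 26.2% to 87.8% |
| 5 | 18.7% to 81.3% |

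The intervals are wide, but they would answer the question in section 1 to the extent that ten patients allow.

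**Step 3. Whether failures raise the chance of a utility claim.** Assume no bias, normal and independent differences, and failure unrelated to the size of the difference. The documents give no SD of the difference, so a range is used. With q = P(|difference| ≥ 2 mm) = 2[1 − Φ(2/SD)] and k pairs, the chance that noise alone meets the rule is 1 − (1 − q)^k. If 4 of 10 patients are unreadable at both time points, k = 6 × 2 = 12.

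| SD (mm) | q | 20 pairs | 12 pairs |
|---|---|---|---|
| 0.75 | 0.0077 | 0.14 | 0.09 |
| 1 | 0.0455 | 0.61 | 0.43 |
| 1.5 | 0.1824 | 0.98 | 0.91 |
| 2 | 0.3173 | 1.00 | 0.99 |

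At an SD of 1 mm, for example, 1 − (1 − 0.0455)^20 = 0.61 and 1 − (1 − 0.0455)^12 = 0.43. In every row the chance falls as readings are lost. If each reading independently has an 80% chance of being unreadable, the chance is 1 − (1 − 0.2q)^20, which is 0.03, 0.17, 0.52 and 0.73 for the four SDs. Failure makes the rule harder to meet but does not block it.

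**The case against.** Three points can fairly be made on the other side.

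*The plan never says that failed readings are excluded.* This is correct: it is silent. Exclusion is an inference, drawn because a difference cannot be formed without an OPIE reading and no other handling is given. It should be described as the default, not as a stated rule.

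*The number of readings obtained could be recovered.* Enrolment is fixed at 10 and the intended OPIE readings at two per patient, so a count of successes could be taken from the planned dataset. A reader might infer that the trial is unable to answer its question on visualisation; the documents do not support that. What stands is that the plan neither defines a readable image nor commits to reporting the count.

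*The utility rule is the real source of false claims.* A reader might take the 43% in the working (12 pairs, SD 1 mm) as the harm done by image failure. It is not. On the same assumptions the figure is 61% with all 20 pairs readable. That chance belongs to the rule that any single 2 mm difference suffices, which is a separate matter. What stands here is narrower: the rule ignores how often the probe failed.

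That the formal objective in section 2 is utility, not visualisation, does not remove the point. A probe that often gives no reading has limited utility, and section 1 names visualisation explicitly.

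**Conclusion.** The point holds, and the plan should be changed. A question that section 1 poses has no outcome. Failed readings have no stated handling and would by default leave the mean, the SD and the 2 mm rule. Utility could be declared from as few as 1 readable pair of 20, which follows from the rule's wording alone.

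How likely such a declaration is cannot be fixed from the documents, because it depends on an SD and a failure rate that they do not give. No probability should be quoted as the size of this defect. Its size is the information lost: without the count a reader cannot distinguish 10/10 readable (lower bound 69%) from 6/10 (26% to 88%). The intervals are exact and treat the patients as independent.

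**What to change.** - Add a feasibility outcome, co-primary or key secondary: the number of patients with a readable OPIE thickness at the target site out of all attempted, separately before and after resection, each with an exact 95% CI. Either status supplies the same information.
- Define readable in advance, for instance as both septal borders identifiable.
- Keep every attempted patient in the denominator and count an unreadable or abandoned attempt as a failure.
- State the number of pairs behind each mean and SD.
- Make any conclusion of utility conditional on the readable rate and report the two together, so that a 2 mm difference alone does not suffice. Reporting the count beside the difference without this link would leave the gap open. The investigators should set the threshold. As an illustration only, requiring at least 8 of 10 readable would be met with probability 0.055 at a true rate of 50% and 0.930 at 90%.

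The cost is one yes/no field per reading and one line of analysis, with no added patients or procedures. The reported result may look less favourable.

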## **2. OBJECTIVES**

The objective of this research project is to assess the utility an ultrasound probe that is currently clinically used to assess pituitary anatomy, the Hitachi-Aloka high resolution pituitary transducer to measure left ventricular (LV) septal thickness during cardiopulmonary bypass in the performance of surgical septal myectomy.

## **3. RATIONALE**

There is currently no way to monitor the depth of surgical septal myectomy during the on-pump period in the OR. This is because the heart is empty of blood and transesophageal echocardiography (TEE) imaging is impossible. Also epicardial imaging is impossible. The brochure (attached separately) shows the probe we believe will let us image the septum. It may make the surgical procedure more accurate and decrease complications of “too little myectomy” or “too much myectomy”. Both can decrease the need for reoperation which is currently a risk of myectomy 1-2%. The probe is a sterile one-time-use device. The transducer itself is 2.9 mm in diameter. We have tested the probe in a simulation similar to that we will encounter during Hypertrophic Cardiomyopathy (HCM) surgery and there was excellent visualization of muscular thickness with 1:1 correlation with conventionally measured muscular wall and the ultrasound visualized thickness.

## **4. METHODS AND PROCEDURES**

Subjects will be volunteer patients with hypertrophic cardiomyopathy who will be undergoing myectomy from the HCM Program. Before cardiopulmonary bypass the anterior septal thickness at the point of mitral-septal contact will be measured by TEE in 120 degree view. The distance from the aortic annulus of this location will also be noted. With OPIE the PI will measure this thickness at the

site of mitral-septal contact as assessed by the location of the contact lesion (callous) and confirmed by the cm below the aortic annulus. After resection the residual thickness of the septum will be measured both by OPIE and by post-cardiopulmonary bypass TEE. The thickness of the surgical specimen will be measured. The differences between the OPIE and TEE measured septal thicknesses provide the primary data points for the statistical analysis.

We estimate that the cardiopulmonary bypass time of the OPIE will be prolonged 3 minutes. This may be offset by faster myectomy time gained by more confidence of septal thickening. Length of stay should not be prolonged.

We will enroll 10 subjects in this pilot study. Subject participation will be complete after their hospitalization for surgery. No follow-up visits are necessary, outside of the routine post-op care.

In general, results from studies, which use data, collected as part of this research will be preliminary, and the clinical implications of any findings may not be understood for years. Therefore, individual study results will not be disclosed to the patient and/or his or her healthcare provider(s). Data will be stored in a database housed within the Department of Cardiothoracic Surgery. The above mentioned database will be stored until the end of the study in a password protected secure computer server accessible only by the principle investigator, co-investigators and research staff listed for this project.

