#### **9. STUDY MANAGEMENT AND PERSONNEL**

The Principle Investigator for this research project will analyze and store the data. The Principle investigator will store the data on a secure NYU server on a locked computer, where access will be restricted to the PI and other members of the study.

All Investigators and study personnel involved in this study have completed the appropriate human subjects' research training (NYU CITI module).

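### The second reading of each OPIE-TEE pair is not protected from knowledge of the first, and no value is fixed when it is taken

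*Combined protocol and SAP*

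**What the plan says.** Section 4 (Methods and Procedures) sets the order of measurement. For the first pair, "Before cardiopulmonary bypass the anterior septal thickness at the point of mitral-septal contact will be measured by TEE in 120 degree view", and the distance of that point from the aortic annulus is noted. The next sentence begins "With OPIE the PI will measure this thickness at the" and goes on to name the site, matched by the contact lesion and the annulus distance. For the second pair, "After resection the residual thickness of the septum will be measured both by OPIE and by post-cardiopulmonary bypass TEE". Section 4 then states that "The differences between the OPIE and TEE measured septal thicknesses provide the primary data points for the statistical analysis".

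Section 3 (Rationale) explains why the two techniques cannot be used together on pump: "This is because the heart is empty of blood and transesophageal echocardiography (TEE) imaging is impossible".

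The paragraph on sample size and data analysis makes the OPIE-TEE difference the primary outcome, to be reported as mean and standard deviation. It also sets a rule for utility: a difference of at least 2 mm, in either direction, "between any single OPIE measurement and the TEE measurement either before cardiopulmonary bypass or after cardiopulmonary bypass". It adds that "even a 2-4 mm difference in just one patient (10% of patients) is deemed essential information".

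Section 9 says "The Principle Investigator for this research project will analyze and store the data".

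The plan does not say who reads TEE at either time, or who takes the OPIE reading after resection.

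**The concern.** A difference between two methods is a clean measure of their disagreement only if each reading is made without the other in view. Here one reading of every pair is made when the other already exists. A reader who knows the first value could, without intent, bring the second closer to it or move it away. A first value that is not fixed when taken could also be adjusted once the second is known.

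Either effect would alter the reported mean and SD of the differences. Because one difference of 2 mm decides the utility statement, a small shift in a reading near that limit could also alter the conclusion. In the first pair the exposed reader is the PI, who also analyses the data, so the plan has no separation of roles that would compensate.

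**Working it through.** **Step 1. Which readings are exposed.** 10 patients x 4 readings = 40 values, forming 10 x 2 = 20 pairs.

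| Pair | First reading | Second reading (exposed) |
|---|---|---|
| Before resection | TEE before bypass, reader not named | OPIE, read by the PI |
| After resection | OPIE, reader not named | TEE after bypass, reader not named |

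The first reading of each pair is taken before its partner exists, so it can be influenced only by later revision. The exposed second readings are 10 OPIE and 10 TEE values, 20 of the 40.

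**Step 2. Whether other text gives protection.** Section 4 withholds individual study results from the patient and healthcare providers. That concerns release of results; it does not govern what a reader knows at the time of measurement. The Data Safety Monitoring Plan assigns safety review only. Section 4 also has the surgical specimen measured, but states no masking and no analysis for it. Using the annulus distance to match the site is legitimate and is not part of this point.

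**Step 3. The plan's own figures.** One patient in 10 is 10%, as stated. The sample size of 10 has no stated alpha, power, SD or effect size, so it cannot be reproduced.

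**Step 4. How far a shift in the second reading could matter.** The documents give no SD and no size of influence. The following are assumptions: differences are Normal with mean 0 and SD s, the 20 pairs are independent, and a share a of each difference is removed (negative a means widened).

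Per pair: p = 2 x [1 - Phi(2 / (s(1 - a)))]

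Meeting the rule: P = 1 - (1 - p)^20

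Worked case, s = 1.0 mm:
- a = 0: p = 2 x [1 - Phi(2.000)] = 0.0455; P = 1 - 0.9545^20 = 0.606
- a = 0.05: argument 2/0.95 = 2.105, p = 0.0353; P = 0.512
- a = 0.10: argument 2/0.90 = 2.222, p = 0.0263; P = 0.413
- a = 0.25: argument 2/0.75 = 2.667, p = 0.0077; P = 0.143
- a = 0.25 at one time point only: P = 1 - (1 - 0.0455)^10 x (1 - 0.0077)^10 = 0.419
- a = -0.25: argument 2/1.25 = 1.600, p = 0.1096; P = 0.902

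Other SDs, chance of meeting the rule:

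| SD (mm) | unaffected | all shrink 5% | all shrink 10% | all shrink 25% | one time point shrinks 25% |
|---|---|---|---|---|---|
| 1.0 | 60.6% | 51.2% | 41.3% | 14.3% | 41.9% |
| 1.5 | 98.2% | 97.0% | 94.9% | 79.2% | 93.9% |
| 2.0 | 99.9% or more | 99.9% | 99.8% | 98.2% | 99.7% |

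With a within-patient correlation of 0.5 (200,000 simulated trials, s = 1.0 mm), the chance is 58.0% unaffected and 13.7% with 25% shrinkage, so independence is not what drives the contrast. With a mean offset of 3 mm the rule is met almost surely at every SD tried (0.5 to 2.0 mm), but 25% shrinkage would still reduce the reported mean to 3 x 0.75 = 2.25 mm.

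The high unaffected values come from the any-of-20 rule, which is a separate matter. Only the contrast within a row bears on this point.

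**The case against.** The strongest reply has four parts.

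1. Only half the readings are exposed, and nothing suggests that first values would be revised. The first half of this stands: the point is limited to 20 second readings. Revision is a possibility that the plan leaves open, not something it describes.

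2. The striking contrast, 61% to 14%, needs an unsourced 25% shift in all 20 pairs at one SD. This stands. With 5% or 10%, or with one time point affected, the fall is much smaller, and at SD 2.0 mm the result hardly changes. Nothing in the documents places the study at any particular SD.

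3. Masking is weakest where exposure is clearest. The PI takes the pre-resection OPIE reading and also cares for the subjects (section 8), so may already know the TEE thickness. This stands for that reading: fixing the TEE value first does not stop the PI from knowing it. It does not apply in the same way to the post-bypass TEE.

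4. This is a 10-patient pilot with descriptive statistics, and section 4 calls its results preliminary. That limits the weight of the point. It does not remove it, because these differences are the primary data and the plan draws a utility conclusion from them.

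A reader might go further and infer that the PI knew the TEE value, or that the readings will be biased in a particular direction. The documents support neither. They are silent on what each reader knows. Influence towards the first value would overstate agreement, and influence away from it would favour the utility rule.

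**Conclusion.** The point holds as a gap in protection of the primary data. The pairs are necessarily sequential, and no text keeps the second reader unaware of the first value or fixes a value once taken. It affects the pre-resection OPIE reading and the post-bypass TEE reading.

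Its size cannot be determined from the documents. Under the stated assumptions, the effect on the utility rule runs from negligible (SD 2.0 mm, or a large true offset) to decisive (SD 1.0 mm with all differences shrunk by 25%). The reported mean and SD would be affected whether or not the rule's result changes. The calculation shows that reader knowledge could matter; it does not estimate how much it will.

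**What to change.** In section 4 and the data analysis paragraph:

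- Record and time-stamp each thickness when it is taken, before its pair is obtained, and allow no later revision of the value used in the primary analysis.
- Have the post-bypass TEE thickness read and recorded without knowledge of the OPIE residual, where this withholds nothing the operating team needs.
- Report as a limitation that the pre-resection OPIE reading may be made with knowledge of the TEE thickness.

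Site matching by annulus distance stays as it is.

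The cost is a few sentences and a little record-keeping for 40 values, with no extra reader, patient or procedure. Masking before resection remains incomplete. The recording step has to be in place before the first case, because it cannot be added after readings have been made.

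### Specimen thickness is measured but has no role in the analysis, and the 2 mm rule credits OPIE with any OPIE–TEE difference although its size cannot show which technique erred.

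*Combined protocol and SAP*

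**What the plan says.** Section 2 sets out to assess the utility of the probe "to measure left ventricular (LV) septal thickness during cardiopulmonary bypass in the performance of surgical septal myectomy". Section 4 (Methods and Procedures) takes thickness before resection by both techniques. It continues: "After resection the residual thickness of the septum will be measured both by OPIE and by post-cardiopulmonary bypass TEE". The specimen follows: "The thickness of the surgical specimen will be measured". The next sentence fixes the primary data: "The differences between the OPIE and TEE measured septal thicknesses provide the primary data points for the statistical analysis".

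The subsection on sample size and data analysis then lists what each patient contributes: "Each of the 10 patients will have 4 measurements(OPIE & TEE before cardiopulmonary bypass and OPIE & TEE after cardiopulmonary bypass". The primary outcome is the TEE–OPIE difference before and after bypass, summarised by mean and SD. Utility is shown by a difference of at least 2 mm, in either direction, "between any single OPIE measurement and the TEE measurement either before cardiopulmonary bypass or after cardiopulmonary bypass". One such patient in ten is enough. The same subsection says: "Accurate myectomy residual thickness is vital for success of this operation".

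The specimen is not mentioned in that subsection. The word appears once more, in section 10, in connection with the key code.

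**The concern.** The rule treats a large OPIE–TEE difference as a point in OPIE's favour. A difference of that size can arise because TEE was wrong, because OPIE was wrong, or because the septum was imaged in two different states. An inaccurate probe could therefore pass as a useful one.

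The bench test in section 3 compared the probe with a conventional, non-ultrasound measurement. The patient study also collects one, for the tissue removed, but states no purpose, measurement site, recording order or analysis for it. Any later use would be chosen after the imaging values were known.

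**Working it through.** **Inputs.** From the documents: 10 patients, two OPIE–TEE pairs each (20 differences), and the 2 mm threshold. The plan's one derived figure reproduces: 1/10 = 10%. The documents give no error SD, bias or depth removed, so every such value below is an assumption. Simulations used 40,000 studies of n = 10, normal errors and a mean of 8 mm removed.

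**1. The rule cannot tell the devices apart.** With unbiased, independent errors, the SD of a difference is √(s_OPIE² + s_TEE²), which is symmetric in the two devices.
- SDs 0.5 and 1.5 mm: √(0.25 + 2.25) = 1.58 mm. P(|d| ≥ 2) = 2[1 − Φ(2/1.58)] = 0.206. P(at least one of 20) = 1 − 0.794²⁰ = 0.990, whichever device has the 1.5 mm SD.
- SDs 0.3 and 1.0 mm: SD 1.04 mm, and the rule is met in 68% of studies either way.

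**2. What the specimen offers.** Let D = (pre − post) − specimen for each device, with pre and post meaning before and after resection. Then SD(D) = √(2s² + s_spec²).
- Specimen SD 0.5 mm: s = 0.5 gives √0.75 = 0.87 mm; s = 1.5 gives √4.75 = 2.18 mm. The two swap if the errors swap.
- Specimen SD 2 mm: √4.5 = 2.12 and √8.5 = 2.91 mm, a much smaller contrast.

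**3. Like-for-like comparison with the readings already planned.** The raw change (pre − post) has variance s_depth² + 2s², where s_depth is the between-patient SD of depth removed. Subtracting the specimen replaces s_depth² with s_spec². Percentage of studies in which a Pitman-Morgan test identifies the noisier device (SDs 1.5 and 0.5 mm):

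| Depth SD (mm) | Raw change | Specimen SD 0.5 | Specimen SD 1 | Specimen SD 2 |
|---|---|---|---|---|
| 0 | 87 | 74 | 48 | 20 |
| 1 | 48 | 74 | 48 | 20 |
| 2 | 20 | 74 | 48 | 20 |

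The specimen helps only when s_depth exceeds s_spec.

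**4. What it cannot do.**
- *Constant offset:* (pre + c) − (post + c) removes c. A 3 mm OPIE offset leaves mean D_OPIE at 0.0 mm.
- *Heart state:* section 3 explains why TEE cannot monitor depth on bypass: "This is because the heart is empty of blood and transesophageal echocardiography (TEE) imaging is impossible". OPIE and TEE therefore see different states. With both devices at 0.5 mm, patient-to-patient state variation of SD 2 mm in the TEE change gives SD(D_TEE) = √(0.5 + 0.25 + 4) = 2.18 mm, exactly the noisy-TEE picture. A 1.6 mm state shift in TEE (all device SDs 1 mm, specimen 0.5 mm) makes only D_TEE's 95% CI exclude zero in 81% of studies.
- *Specimen bias:* a 1 mm bias, with TEE and OPIE SDs of 1.5 and 0.5 mm and specimen SD 0.5 mm, makes only D_OPIE's CI exclude zero in 67% of studies, although the shift is shared. The CI of the paired mean D_OPIE − D_TEE does so in 5%. That contrast equals (OPIE − TEE) pre minus (OPIE − TEE) post, so the specimen cancels.

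**5. Precision.** With device SDs of 1 mm the paired mean has a 95% CI half-width of about 1.4 mm, and its CI excludes zero in 62% of studies with a 1.6 mm one-device shift.

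**The case against.** The case against is substantial, and much of it stands.

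- *The four readings may already do the job.* A reader might infer that, without the specimen, the data say little about which device is noisier. The documents do not support this. If depth removed is nearly constant, the raw changes discriminate better than the specimen does (87% against 74%). The depth SD is not given, so the specimen's added value is possible but not demonstrated.
- *The safest contrast needs no specimen.* This is correct: its mean follows from the pre and post mean differences already planned. The specimen alone contributes the two separate D summaries, which specimen bias and heart state can distort.
- *The remedy does not settle who erred.* This is also correct. A reader might infer that the specimen is a reference standard that would validate OPIE or rank the devices. It measures tissue removed, not residual thickness, and it may be irregular or in pieces.
- *The plan claims utility, not superior accuracy.* A reader might infer an accuracy claim from the 2 mm rule, but the text makes none. The narrower problem remains: a difference caused by OPIE error would still count as utility.
- *This is a 10-patient descriptive pilot.* Agreed, and it limits the weight of the point.

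None of this gives the specimen a stated purpose or makes the rule sensitive to which device erred.

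**Conclusion.** The point holds as a low-cost improvement worth considering. Two facts rest on the text alone: the specimen is measured without a stated use, and the 2 mm rule credits OPIE for a difference whose size is silent on its source. The size of the second (99.0% either way at SDs of 0.5 and 1.5 mm; 68% at 0.3 and 1.0 mm) rests on assumed, unbiased, normal and independent errors; the symmetry itself does not depend on those SD values. The benefit of adding the specimen depends on a depth SD larger than the specimen's error SD, and the documents give neither. The planned differences, means and SDs do not change; what changes is how a 2 mm difference may be read. Residual thickness, the quantity the plan calls vital, stays unverified.

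**What to change.** Add to the subsection on sample size and data analysis, as a secondary descriptive analysis:

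> For each patient we will report D_OPIE = (OPIE pre − OPIE post) − specimen thickness and D_TEE = (TEE pre − TEE post) − specimen thickness, where pre and post mean before and after resection. Mean, SD and 95% CI will be given beside the raw pre–post changes and the paired mean of D_OPIE − D_TEE, which does not depend on the specimen. Specimen thickness will be measured at the contact lesion and recorded before the imaging values are compared; specimens not measurable there will be reported as missing. This analysis addresses measured change only. It cannot detect a constant offset, verify residual thickness, or separate device error from heart state. An OPIE–TEE difference of 2 mm or more will be reported as disagreement between the techniques and will not by itself be taken as showing that OPIE is correct or useful.

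Cost: one paragraph and two measurement rules (site on the specimen, recording order), with no added patients or procedures. Downside: the specimen is an imperfect and possibly biased reference, and precision at n = 10 is low, so a CI that includes zero would not show that the devices agree. The last sentence of the paragraph is worth adopting even if specimens prove hard to measure.
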